Role of FDG-PET CT in the Management of Muscle Invasive Bladder Cancer
NCT04053101
ID: IB2018-TEP vessie
Jan 5, 2017

INTRODUCTION

Bladder cancer is the second urologic cancer in terms of incidence. The prognosis of MIBC is poor, with a 5-year survival rate from 45 to 50% (1). Main prognostic factors are the quality of the surgery (with a complete resection R0), a pelvic LN dissection with at least 10 LN and a pathological Complete Response (pCR) after neoadjuvant chemotherapy (NAC) (2,3). Treatment decisions are taken during a tumor board, based on the staging of local disease, LN status and distant localization.

Usually, CT and less frequently Magnetic Resonance Imaging (MRI) are recommended for LN and metastatic staging of MIBC. For LN staging, CT is used, despite a low reported sensitivity, around 30-53%, but a high specificity between 68 to 100% (6,7). MRI is more accurate for LN staging, mostly by using DWI sequences (sensitivity of 56% and specificity of 94%) (8). FDG-PET CT combines anatomical and metabolic imaging. The sensitivity is usually better for detecting pathological infra centimetric LN, but the specificity is low. In cases of MIBC, several studies have evaluated FDG-PET CT as imaging for initial nodal staging before cystectomy and reported a sensitivity between 29% and 81% and a specificity between 86.7% and 97%, depending on interpretation criteria (9-12). Two meta-analysis evaluated the accuracy of FDG-PET CT in MIBC. The first one found a sensitivity of 57% and a specificity of 92% for preoperative LN staging of MIBC by using FDG-PET CT (13). The second one published in 2018 compared accuracy of CT, MRI and FDG-PET CT for staging bladder cancer (14). MRI and FDG-PET CT had a higher sensitivity (respectively 60% and 56%) compared to CT (40%) while the specificity of all modalities was similar. Other studies evaluated the rate of treatment modification based on the results of FDG-PET CT, around 25% (from 13.5% to 68%) mainly due to the confirmation of metastatic spread (9,15-18). FDG-PET CT has also been indicated to evaluate therapeutic response after chemotherapy (19,20).

To date, FDG-PET CT is not recommended for the staging of MIBC, as a standard of care but rather as an option (21). We aimed to investigate the role of FDG-PET CT and its accuracy in LN staging of MIBC at diagnosis and how it may improve treatment decision.

Patients and Methods

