Patients will be retrospectively included from both the University Hospital and the Cancer Center from Bordeaux. To be included in the study, patients should have undergone a FDG-PET CT at the time of diagnosis of MIBC. Only patients with diagnosis of predominant urothelial carcinoma, \geq pT2 of the bladder will be included.

Clinical data collected: center of reference, date of birth, history of tobacco intoxication, performance status, date of relapse and site of relapse, date of the latest news or date of death and status (alive or dead).

Pathological information (which is the gold standard) included biopsy site, date of biopsy, histology, pathological result of cystectomy and LN dissection (TNM classification, status R, number of LN resected, number of positive LN, necrosis, and presence of pCR after NAC). CT data will be extracted from radiological or medical reports (before and after NAC) and the lesions described will be classified according to the 8th TNM classification, actualized in 2017 (22). RECIST1.1 criteria allowed to describe pathological LN (corresponding to LN with smallest axis greater than 15mm). For metastatic lesion, patients will be classified as “M0” (without metastasis), without suspect ¹⁸FDG intake, or as “M1a” in case of metabolic activity of non-regional LN, and as “M1b” in case of distant metastatic lesions. FDG-PET CT results will be extracted from nuclear medicine reports for the University Hospital, or by exam reviewing for Institute Bergonie exams. Data collected were: size, SUV max, Tumor Lesion Glycolysis for each lesion (tumor, LN or metastasis) and TNM staging. If patients undergo a FDG-PET CT before and after NAC, a metabolic response (such as complete, partial, stable, progressive or dissociated) will be notified. Treatment characteristics will be extracted from the database (chemotherapy regimen, type of surgery (Table 1) and radiotherapy modalities).

Objectives

Objective of this study is to evaluate the performance accuracy of FDG-PET CT for LN staging at the diagnosis of MIBC (before and after NAC and before cystectomy and LN dissection).

Statistical analysis

Qualitative values will be described by total numbers and percentage. Quantitative values will be presented as median, minimum and maximum value, average and standard deviation. For diagnosis accuracy of CT and FDG-PET CT, we will calculate the sensitivity, specificity, false positive rate, false negative rate, Youden index.

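### Accuracy of FDG-PET CT, the only objective, is planned as point estimates without confidence intervals, and the separate CT figures could not support a comparison

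*Combined protocol and SAP*

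**What the plan says.** The Objectives section gives one aim: "Objective of this study is to evaluate the performance accuracy of FDG-PET CT for LN staging at the diagnosis of MIBC". A parenthesis then sets the time frame as "before and after NAC and before cystectomy and LN dissection". No comparison with CT is named as an objective.

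The accuracy analysis is one sentence under Statistical analysis. For CT and FDG-PET CT, "we will calculate the sensitivity, specificity, false positive rate, false negative rate, Youden index". The rest of that section is descriptive: "Qualitative values will be described by total numbers and percentage", and quantitative variables are summarised by median, range, mean and standard deviation.

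Patients and Methods names pathology as the gold standard. It makes an FDG-PET CT at diagnosis a condition of inclusion and sets no such condition for CT. CT findings are taken from radiological or medical reports, before and after NAC.

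The document contains no confidence interval, standard error, precision target, sample size, expected number of node-positive patients or PET-by-CT table.

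**The concern.** This is an estimation study, so the precision of the estimate is part of the answer. The five listed statistics contain only two independent quantities per test: the false negative rate is 1 - sensitivity, the false positive rate is 1 - specificity, and the Youden index is sensitivity + specificity - 1. None of them conveys precision. A sensitivity from a few dozen node-positive patients would be presented in the same form as one from several hundred.

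Two further gaps follow from the same sentence.

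- **CT beside PET.** The same measures are planned for both tests, and the Introduction motivates PET by its higher published sensitivity than CT (56% against 40%). Readers are therefore likely to compare the two columns. Two separate percentages do not show how often the tests disagree in the same patient, and the precision of a paired difference depends on that.
- **Timing.** The objective and the CT data collection both span NAC, but the analysis does not say that results are separated by scan time. In a patient who receives NAC before surgery, a pre-NAC scan is judged against nodes that chemotherapy may have altered. An interval around a pooled figure would not repair that.

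**Working it through.** The plan states no sample size or precision figure, so there is nothing of its own to reproduce. The calculations below are illustrative.

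**Inputs from the Introduction.** PET sensitivity 56-57%, PET specificity 92%, CT sensitivity 40%. Cited range of PET sensitivity: 29% to 81%.

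**Assumptions, not in the documents.** 20, 30 or 60 node-positive (pN+) patients; two node-negative (pN0) patients per pN+ patient; 95% confidence; 40 pN+ patients with both scans for the paired example.

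**1. Sensitivity and specificity.** Exact (Clopper-Pearson) limits for x out of n: lower = the 2.5% point of Beta(x, n-x+1); upper = the 97.5% point of Beta(x+1, n-x).

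| pN+ / pN0 | Sensitivity | 95% CI | Specificity | 95% CI |
|---|---|---|---|---|
| 20 / 40 | 11/20 = 55.0% | 31.5-76.9% | 37/40 = 92.5% | 79.6-98.4% |
| 30 / 60 | 17/30 = 56.7% | 37.4-74.5% | 55/60 = 91.7% | 81.6-97.2% |
| 60 / 120 | 34/60 = 56.7% | 43.2-69.4% | 110/120 = 91.7% | 85.2-95.9% |

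With 20 pN+ patients the sensitivity interval is 76.9 - 31.5 = 45.4 points wide. The cited literature range is 81 - 29 = 52 points wide.

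**2. Youden index.** J = Se + Sp - 1. The pN+ and pN0 patients are separate groups, so Wilson limits (l, u) can be combined:

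- lower = J - sqrt[(Se - l_Se)² + (Sp - l_Sp)²]
- upper = J + sqrt[(u_Se - Se)² + (u_Sp - Sp)²]

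For 11/20 and 37/40 the Wilson limits are 0.342-0.742 and 0.801-0.974, and J = 0.550 + 0.925 - 1 = 0.475.

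- lower = 0.475 - sqrt(0.208² + 0.124²) = 0.233
- upper = 0.475 + sqrt(0.192² + 0.049²) = 0.673

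In the same way, 17/30 with 55/60 gives 0.483 (0.283-0.650), and 34/60 with 110/120 gives 0.483 (0.343-0.607).

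**3. PET beside CT.** Take 40 pN+ patients, PET positive in 22 (55%) and CT positive in 16 (40%). The difference is (22 - 16)/40 = 15 points whatever the overlap. Let b be the number positive on PET only and c the number positive on CT only; then b - c = 6 in every case. If the tests were independent, b would be 22 × 24/40 = 13.2 and c would be 18 × 16/40 = 7.2.

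| b vs c | Tango score 95% CI (points) | Exact McNemar p |
|---|---|---|
| 6 vs 0 (extreme) | 4.9 to 29.1 | 0.031 |
| 7 vs 1 | 1.4 to 30.1 | 0.070 |
| 9 vs 3 | -2.2 to 32.1 | 0.146 |
| 13 vs 7 (about independent) | -7.1 to 35.6 | 0.263 |

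All four rows would print as 55% and 40%. At 7 vs 1 the interval excludes zero while the exact p-value exceeds 0.05, so one of the two has to be named in advance as the main result.

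**The case against.** The strongest reply has four parts.

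- **Counts may be enough.** Nodal status by scan and by pathology is qualitative, and the plan promises numbers with percentages for qualitative values. With the 2x2 counts a reader could rebuild the single-test intervals and the Youden interval. This is correct as far as it goes. However, the promise is general and is not tied to the accuracy tables, and an author should not leave readers to compute the uncertainty of the main result. Counts for each test separately would still not give the paired interval.
- **No comparison is planned.** True, so the CT point is conditional on the two sets of figures being shown or read together. It concerns the planned output only. Where patients have both scans, the underlying data could support a contrast.
- **The magnitudes are assumed.** Also true. They show what group sizes of this order would do and are not evidence that this cohort is small. The absence of planned intervals does not depend on them.
- **NAC timing is a different issue.** It is about possible bias, the parenthesis in the objective can be read in more than one way, and its effect is not quantified here. It still belongs with this point, because an interval is only useful around an estimate whose scans and reference standard are defined.

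The particular interval methods are a matter of choice. Wilson limits would serve as well as exact ones for sensitivity and specificity.

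**Conclusion.** The concern holds. The accuracy analysis for the sole objective is a closed list of five point statistics, and no measure of uncertainty is planned anywhere in the document. The point estimates are not biased by this, so it is a point that should be corrected rather than one that invalidates the study.

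On the stated assumptions, the unreported uncertainty in sensitivity runs from about 45 points of interval width with 20 node-positive patients to about 26 (69.4 - 43.2) with 60. For the Youden index the widths are 0.44 (0.673 - 0.233) and 0.26 (0.607 - 0.343). Confidence is high that intervals are missing. The CT point depends on side-by-side presentation, and the effect of mixing scan times is unquantified.

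**What to change.** Add the following to the Statistical analysis section, with the patient as the unit:

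1. For each test, report the 2x2 counts against nodal pathology, sensitivity and specificity with exact 95% intervals, and a 95% interval for the Youden index (for example, combined Wilson limits).
2. Report results separately by scan timing relative to NAC. Do not pool pre-NAC scans judged against post-NAC nodal pathology with scans that NAC does not separate from the pathology.
3. If PET and CT are shown side by side or compared, restrict this to patients with both scans at the same time point and nodal pathology, and state how many qualify. Give the PET-by-CT cross-tabulation and the paired difference with a 95% score interval as the main result, with exact McNemar as support, separately in pN+ and pN0 patients.

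The cost is a few lines of plan and code on data already due to be collected. The timing groups and the paired subset will be smaller than the cohort, so intervals will be wide and conclusions will look less certain.
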